## Application and Submission Instructions (IRB Form 101)

**DO NOT CHANGE THE FORMATTING OF THIS DOCUMENT.**  
**DO NOT USE THIS FORM ON A MAC; IT WILL CHANGE THE FORMATTING OF THIS DOCUMENT, WHICH WILL MAKE IRB REVIEW MORE DIFFICULT AND LENGTHIER.**

 - FOR CHECKBOXES - DOUBLE CLICK THE BOX - CHOOSE 'CHECKED'; HIT OK.

 - FOR TEXT BOXES - CLICK IN SHADED BOX AND TYPE.

*The Principal Investigator (PI) is required to use this form to submit new research projects to the IRB. This form is to be used when there is interaction with human subjects.*

**Each section of the application requires a response.**

Ensure all responses are consistent with the approved funded project, the informed consent, and the HIPAA Authorization, if applicable. **Ensure all sections of the application are completed or marked "Not Applicable."**

**One single-sided hard copy of this application form must be submitted to the IRB Office with ALL required signatures.**

The **electronic version** sent to the IRB Administrator **must** be **Word** documents, **unless** the form is already a PDF.

This application form was designed to be self-explanatory with embedded instructions and guidance to follow as the form is being completed. However, if any questions arise as the form is being completed, contact one of the IRB Administrators, [[contact]](mailto:[contact]) or [[contact]](mailto:[contact]).

**THERE MAY BE OTHER DOCUMENTS YOU WILL NEED FOR YOUR PROJECT, SUCH AS THE RESEARCH STAFF FORM, INFORMED CONSENT, HIPAA AUTHORIZATION/REVOCATION FORMS, ETC., WHICH CAN BE OBTAINED FROM**

## SECTION 3: PROJECT OVERVIEW

1.	What organization is funding this study? (Check all that apply)
	 CSP  CSR&D  HSR&D  RR&D  BSLR&D  QUERI
	 VHA Central Office  Private Nonprofit: Please specify: 
	 Department of Defense (DoD)  Commercial Sponsor: Please specify: 
	 None; If none is checked, provide justification why there is no funding source. 
	Funding Agency Project number: HX002509-01A1
2.	What are the research questions or hypotheses to be studied? The purpose of this research study is to evaluate the feasibility of a full-scale efficacy randomized control trial (RCT) of SUMMIT, a multi-component web program designed to enable Veterans to safely taper opioids.
	The study will examine the feasibility of using the SUMMIT app in conjunction with a motivational interviewing session in opioid tapering, compared to only using an already established mobile application (Manage My Pain).
	We hypothesize that the proposed feasibility trial will support a future definitive large-scale trial.
3.	Describe the relevance to Veterans of studying the above questions or hypotheses and the importance of the knowledge this project is likely to generate: Veterans have approximately double the rate of opioid overdose compared with non Veterans. (3) Along with the myriad potential adverse events (AEs) associated with long-term opioid therapy (LTOT), mounting evidence suggests it has modest or absent benefit. The first pragmatic long-term randomized control trial (RCT) comparing an opioid-intensive to an opioid avoidant chronic pain management strategy found no improvement in chronic pain outcomes in

*Veterans and double the side effects at 12 months. Guidelines recommend tapering LTOT when harm outweighs benefit; observational data suggest improved quality of life among persons who successfully taper.*

*While guidelines recommending against LTOT initiation should help prevent future harms, hundreds of thousands of Veterans currently on LTOT are left vulnerable as there are insufficient resources to help them taper and/or ultimately discontinue LTOT. To afford a safe, veteran-centered tapering strategy to those currently prescribed LTOT, programs must be developed to extend the reach of face-to-face encounters with health professionals. Thus, we are developing SUMMIT as an ancillary intervention to support, reinforce, and complement provider-initiated opioid tapering initiatives across the VHA.*

4. **What research methods will be used in the project? (Check all that apply)**

 Surveys/Questionnaires	 Interviews	 Audio Taping
 Behavioral Observations	 Chart Reviews	 Video Taping
 Focus Groups	 Randomization	 Double-Blind
 Control Group	 Placebo	 Withhold/Delay Treatment
 Specimen Collection	 Deception	 Other (Specify):

5. **Does the project involve usual care? Yes  No**  - If no, skip to question 6.

5.1. **If yes, answer the following additional questions:**

5.1.1. **Who will provide the usual care, i.e., the study team or the participant's health care provider?**

5.1.2. **Clearly differentiate what is usual care and what procedures and/or interventions are being performed solely for research purposes. Indicate if usual care is limited to one arm of the study or if it is being delivered to all participants:**

**Research procedures:**

**Usual Care:**

6. **Does this project involve international research? Yes  No**

**NOTE:** International research does not include studies in which VA is only one of multiple participating sites where the overall study-wide PI is not a VA investigator.

7. **Does this project involve collaborative research? Yes  No**  - See below

7.1. **If yes, delineate which research activities will be conducted as the VA portion of the overall collaborative research study:**

*West Haven will only be participating in the data analysis. West Haven was the original site that had received funding. The implementation site for the study is the Philadelphia VA.*

**NOTE:** Collaborative studies do not include studies conducted under a Cooperative Research and Development Agreement (CRADA) with pharmaceutical companies or other for-profit or non-Federal partners.

## SECTION 4: POTENTIAL RISK/BENEFIT ANALYSIS

1. Indicate the potential risk level of the project: (Minimal Risk is defined as "the probability and magnitude of harm or discomfort anticipated in the research are not greater in and of themselves than those ordinarily encountered in daily life or during the performance of routine physical or psychological examinations or tests.")

Minimal  Greater than Minimal

**NOTE:** The IRB will make the final risk level determination.

2. What are the potential risks or harms for participants in this project?

(List in bullet or number format)

- Psychological: The Veteran subjects may risk distress from considering opioid tapering. The study team will attempt to mitigate this risk through clear explanation of the study goals and risks prior to subject participation.
- Social: There may be some stress regarding potential loss of confidentiality on the part of subjects that are part of the motivational interviewing, which the study team will attempt to mitigate.
- Confidentiality and Privacy: There is some risk of confidentiality. Efforts by the study team will be made to minimize this risk by following protocols that will keep all research documentation secured.

**NOTE:** Risks or harms can be physical, psychological, financial, social, or legal. They may involve breaches of confidentiality and privacy. Do not include the risks of usual care unless usual care is part of the research interventions being performed.

3. What are the anticipated benefits, if any, to participants or to society from this project?

(List in bullet or number format)

- Participants may need less opioid medication to manage pain
- Participants may experience improvement in overall functioning.
- Veterans may also not directly derive any benefit from participating in this research project. However, if this approach is effective, it could have tremendous benefits for society if adopted on a wide scale to help individuals effectively taper their opioid dosage.

4. Briefly describe the procedures for the orderly withdrawal or termination of subjects if this study involves any medical therapy. N/A

5. Will any of the following be administered to participants or will they be exposed?

	YES	NO
Ionizing Radiation		
Radioactive Materials		

6. Check one of the boxes below based on your study design and provide the references from the protocol for the information in the table:

Prospective Study  Retrospective Study  Both

**NOTE:** If retrospective is checked, some of the below categories may not apply and can be marked as "Not applicable."

Safety Issues	Reference the protocol page and section.	If not referenced in the protocol, cite document type, page and section where it is referenced.
What Safety Information is Collected	N/A	

How will Safety Information be collected	N/A	
Frequency of Safety Data Collection	N/A	
Safety Conditions that Trigger Immediate Suspension of Research	N/A	
Procedures to notify participants or PCP of findings affecting participants' health or welfare	Section 16, 10.1; 11.1; 13.3	
Procedures to minimize risk	Section 16	
Inclusion Criteria	Section 16, 7.1	
Exclusion Criteria	Section 16, 17.1	

7. Will an independent Data Safety Monitoring Board (DSMB) or a Data Monitoring Committee (DMC) monitor the project? Yes  No

7.1. If yes, provide a description of responsibilities to include frequency of meetings:

7.2. If no, provide the protocol section and/or page where the data safety and monitoring plan is described, to include statistical tests to be used for analyzing the safety data to determine if harm is occurring.

*The PI will be responsible for monitoring the study. All participants will be given anticipatory guidance on when to seek medical attention. In addition, participants will be asked to report to the study team any events they feel resulted from participation in the study. They can either present in person or call on the study team. Study staff will contact the participant to collect any information on the issue and then the PI will review and determine whether it is okay to proceed, further investigation is needed, or the participant should stop the study. The PI will review all report of adverse events within 24 hours of their occurrence and on a monthly basis determine if a change in protocol is indicated due to the occurrence of adverse events.*

8. If the PI is not a clinician, is there an appropriately credentialed and privileged clinician who has been designated as a member of the study team to make required decisions to help protect the health of the subject, review data on adverse events, and report new findings? Yes  No  N/A

9. How will you manage information from participating sites that might be relevant to participant protection and describe how that information will be conveyed to the IRB (i.e., reports of problems, interim results)?

*Participating site (VACHS, West Haven campus) will not be involved in the collection of data. Any problems at VACHS such as theft, loss and unauthorized access of records, or evidence of harm will be reported immediately to the PO, ISO, and IRB. Data will be shared with the West Haven via through shared folder on the CHERP server.*

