2.2. What is the schedule of payments, i.e., one-time or after specific visits?

\$5 for bi-weekly surveys (up to 18 times over 9 months) and

\$25 for quarterly surveys (up to 4 times over 9 months)

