***If the project does not fit into one of the above categories, it does not qualify for expedited review.***

## SECTION 14: ABSTRACT

- Objectives(s):** *The purpose of this study is to evaluate the feasibility of a full-scale efficacy randomized control trial (RCT) of SUMMIT (), a multi-component web program designed to enable Veterans to safely taper opioids.*
- Research Design:** *The study design is a 9-month, randomized, two-arm, parallel, open-label feasibility trial. Eligible participants will be randomized to a brief single Motivational Interview (MI) session and SUMMIT versus a pain monitoring app, Manage My Pain App. All participants will be provided a referral to speak with a clinical pharmacy specialist about their medications and options for tapering. Feasibility and outcomes planned for a full-scale RCT will be collected at one-, three-, six-, and nine-months post-intervention. Opioid dose and AEs will be collected biweekly. Given the urgency to develop effective programs to support tapering efforts, an interim analyses will be conducted at three months to evaluate trends in the recruitment rate, use of SUMMIT, and opioid dose reduction. If positive, results of these analyses will expedite the onset of the planned full-scale RCT.*

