#### 4. Study Procedures

##### 4.1. Study Design

4.1.1. Describe experimental design of the study. Include sequential and/or parallel phases of the study, including durations, and explain which interventions are standard of care.

*The study design is a 9-month, randomized, 2-arm, parallel, open-label feasibility trial. Eligible participants will be randomized to a brief single Motivational Interviewing (MI) session and SUMMIT versus a pain monitoring app. All participants will also be provided a referral to speak with a clinical pharmacy specialist about their medications and options for tapering. Feasibility and outcomes planned for a full-scale RCT will be collected at one-, three-, six-, and nine-months post-randomization. Opioid dose and adverse events (AEs) will be collected bi-weekly. We will send the link to the questionnaire to the participant if they have given permission to contact via email, otherwise we will send them the link via text, or read it aloud to them. Given the urgency to develop effective programs to support tapering efforts, we will perform interim analyses at three months. If positive, results of these analyses would expedite onset of the planned full-scale RCT.*

*Eligible patients on long term opioid treatment (LTOT) or on buprenorphine will be identified through VA Corporate Data Warehouse (CDW). Receipt of opioid medication will be defined as any dispense of a VA formulary category CN101 drug. Veterans having liquid methadone dispensed in the previous six months will be excluded. Because all methadone for the treatment of OUD is dispensed at federally licensed opioid treatment programs, we will cross check all methadone dispenses with stop code 523, the code used exclusively in those programs. For Veterans who remain eligible, a focused electronic medical record (EMR) review will be conducted to determine whether the Veteran is currently receiving liquid methadone or participating in a concurrent pain or opioid-related research study, and to check for evidence of hearing or visual impairments (not corrected with hearing aids or glasses), cognitive impairment or psychiatric condition. A list of eligible Veterans will be compiled into an Excel file and saved on the secured CHERP server. This list of potential subjects will NOT be printed out.*

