## 8. Study Evaluations

8.1. Describe all evaluations to be conducted (including screening; tests/questionnaires that will be administered; any procedures that subjects will be required to complete) and data collection methods. Include materials as an appendix or separate attachment.

The following questionnaires will be delivered through REDCap by the study coordinator at the outset of the study, and then every 6 weeks over the course of the study: Baseline Assessment, Daily Opioid Dose, Prescribed Opioids Difficulties Scale, PHQ-8, GAD-7, Modified Social Support Survey, Change Questionnaire, BIRS-24, PROMIS-29 Profile v2.0, and WHO 5-Item Well Being Scale. Participants will complete the surveys with the study coordinator, who will enter the responses into REDCap.

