**13. Communication Plan for Multi-Site Studies or Studies being done at Non-CMCVAMC Locations**

N/A; skip to question 14

**13.1. Include plan for ensuring all required local site approvals are obtained and notifying the Director of any facility where the research is being conducted but the facility is not engaged.**

*All current documentation of VA IRB approvals will be stored in the VA secure server (\vhaphifpccherp.v04.med.va.gov\shares2\[name]) and [name] from the West Haven VA will upload any local site approval documents.*

**13.2. Include plan for keeping all engaged sites informed of changes to the protocol, informed consent, and HIPAA authorization.**

*Monthly team meetings will be held with the PI and study staff to discuss the study progress (including any changes to the protocol, informed consent, and HIPAA authorization).*

**13.3. Include plan for informing local sites of any Serious Adverse Events, Unanticipated Problems, or interim results that may impact conduct of the study.**

*Any SAEs, Unanticipated Problems or interim results that may impact conduct of the study will be immediately discussed with the other study site (West Haven VA) and reported to the CMCVAMC IRB within 5 business days of discovery. We will use the CMCVAMC serious-adverse event form for reporting SAEs, UADEs, and any other unanticipated/unexpected problems. We will also use the CMCVAMC Protocol Deviation form for reporting any protocol deviations. Any adverse event would be reported to the IRB at continuing review.*

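### The passages on adverse-event collection conflict, and a 24-hour review clock that starts at occurrence fails for most events first learned of at a two-weekly survey

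*Combined protocol and SAP*

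**What the plan says.** Five places bear on AE collection.

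- **Section 16, 4.1.1:** "Opioid dose and adverse events (AEs) will be collected bi-weekly". The abstract (Section 14) agrees: "Opioid dose and AEs will be collected biweekly". Neither limits this to one arm or to events blamed on the study.
- **Section 4, item 6, safety table:** the row "Frequency of Safety Data Collection" is answered N/A. So are the rows for what safety information is collected, how it is collected, and what would trigger suspension. The column asks for a protocol reference, and the column for an alternative source is blank.
- **Section 4, item 7.2 (the monitoring plan):** "participants will be asked to report to the study team any events they feel resulted from participation in the study", in person or by phone. Staff then contact the participant, and the investigator reviews. The review time is "The PI will review all report of adverse events within 24 hours of their occurrence", and a monthly look decides whether the protocol should change. The two-weekly collection is not mentioned.
- **Section 16, 8.1:** a list of questionnaires given "at the outset of the study, and then every 6 weeks over the course of the study". No AE form is on it.
- **Section 16, 13.3:** serious and unanticipated events are "reported to the CMCVAMC IRB within 5 business days of discovery". That clock starts at discovery; 11.1 also counts five business days from discovery for deviations and unanticipated problems.

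**The concern.** The people running the study cannot follow all of these passages at once. Staff working from item 7.2 and 8.1 would solicit no AEs. Staff working from 4.1.1 would know the frequency but have no named form.

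If item 7.2 became the working rule, an event would enter the record only when the participant judged that the study caused it. Events without that attribution would not be requested, so the record would be incomplete by construction. The trial is open-label, and the motivational interview, SUMMIT and the optional peer contact belong to one arm only. Participants' readiness to connect an event with the study could therefore differ between arms, and so could the counts.

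Item 7.2 also makes the investigator responsible for monitoring and for a monthly decision on protocol change in the light of AEs. That decision is only as good as the data behind it. A review deadline that scheduled collection usually cannot meet adds a stated rule that would be broken routinely.

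**Working it through.** **Inputs.** Collection every two weeks (4.1.1, abstract); "bi-weekly surveys (up to 18 times over 9 months" (Section 9, item 2.2); review within 24 hours of occurrence (item 7.2); 64 participants randomized 1:1, so 32 per arm (Section 16, 9.1 and 4.1.1). The plan states no computed safety figure to reproduce.

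**Step 1: what bi-weekly means.** 18 surveys × 14 days = 252 days = 36 weeks, or nine four-week months. Twice a week over 36 weeks would be 72 surveys. The payment total agrees: 18 × $5 + 4 × $25 = $190, as Section 9, item 2.3 states. So the interval is 14 days.

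**Step 2: the passages side by side.**
- Frequency: two-weekly in 4.1.1 and the abstract; N/A in the safety table; none in item 7.2.
- Route: not described in 4.1.1; volunteered and filtered by the participant's attribution in item 7.2; N/A in the safety table.
- Instrument: none named anywhere. Section 8.1 also puts daily opioid dose on its six-weekly list, whereas 4.1.1 pairs dose with AEs every two weeks. So 8.1 does not describe the two-weekly survey.

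**Step 3: the 24-hour clock.** Assume that events fall uniformly over an interval of L = 14 days, that surveys are completed on time, and that review follows at once.
- Share of events within 24 hours before the next survey = 1/L = 1/14 = 7.1%.
- Share already older than 24 hours = 13/14 = 92.9%.
- Mean lag = L/2 = 7 days; maximum 14 days.

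Now let a share v of all events be reported at once by phone or in person, with the rest first learned of at the survey. The documents do not give v, so a range is shown. Share reviewable in time = v + (1 − v)/14:
- v = 0: 7%
- v = 0.25: 0.25 + 0.75/14 = 30%
- v = 0.50: 0.50 + 0.50/14 = 54%
- v = 0.75: 0.75 + 0.25/14 = 77%
- v = 1: 100%

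If the clock started at receipt of the report, the lag between event and survey would not count, and the target could be met for every reported event.

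**Step 4: what volunteered reporting alone could do to the arms.** This is illustration only; every input except the 32 per arm is assumed. Take the same true AE risk of 40% in both arms. Observed risk = true risk × share reported.
- Reporting 80% v 40%: 32% v 16% observed, about 10 v 5 participants of 32.
- Reporting 70% v 50%: 28% v 20%, about 9 v 6.
- Reporting 50% v 50%: 20% v 20%. Half the events are missed, but the arms do not differ.

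Incomplete data follow directly from the attribution filter. A difference between arms needs the further assumption of unequal reporting.

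**The case against.** The strongest reply is that two-weekly collection and volunteered reports can coexist as two routes. Item 7.2 never says that its route is the only one, and 4.1.1 carries no attribution limit. If both are run, and the two-weekly questions are the same in each arm, solicited AEs need not differ by arm. This stands, and it rules out the inference that AE data will be arm-dependent. It does not remove the need to reconcile: no passage links the two routes, and the monitoring plan relies on the volunteered one.

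Second, the N/A entries sit in a column asking for a protocol reference, so they can be read as a failed cross-reference and not as a statement that nothing is collected. That is fair. The entry is still wrong, because 4.1.1 gives a frequency that could have been cited, and other rows of the same table do cite Section 16.

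Third, a reader might infer that the 24-hour target is impossible. It is not: a promptly phoned event can be reviewed in time, and the word their in that sentence could grammatically refer to the reports. That ambiguity is itself a reason to state when the clock starts. The clock also has no bearing on which events are captured or on balance between arms.

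Fourth, a reader might take the six-week schedule in 8.1 as a 42-day detection delay for AEs. The documents do not support this, because 8.1 lists no AE form and so sets no AE interval.

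Fifth, it would be wrong to say that only one arm discusses tapering. A pharmacy referral covering tapering options is offered to everyone, which narrows the contrast between arms. The interview, SUMMIT and peer contact remain specific to one arm.

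**Conclusion.** The point holds as a conflict between passages that must be reconciled, together with a review clock that does not fit the collection schedule. About 93% of events first learned of at a two-weekly survey would miss review within 24 hours of occurrence. That figure assumes events uniform over 14 days, surveys on time and immediate review. Across all events, the share in time depends on how many are phoned in at once, which the documents do not say.

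If monitoring follows item 7.2 alone, unattributed events are not requested. Differential reporting by arm is then a plausible risk whose size cannot be derived from the documents; the figures in step 4 show only how it would arise. A reader might also infer that planned inputs for the full-scale trial would be distorted. The analysis section (Section 16, 9.2) does not name AE rates among what will inform that trial, so the case rests on safety oversight and complete ascertainment. No sample size, power or alpha figure is affected.

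**What to change.** - Add the same short set of solicited AE items to the planned two-weekly survey in both arms, asked whether or not the participant connects the event with the study. Keep volunteered reports as an additional route.
- Name those items and their two-weekly schedule in Section 16, 8.1.
- Have Section 4, item 7.2 refer to the two-weekly collection, and replace N/A in the safety table for what, how and how often with references to it.
- Start the 24-hour review clock when the study team receives the report.
- The sponsor must also reconcile the N/A entry for suspension triggers. No trigger is proposed here.

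The cost is a few extra items on a survey that is already planned and paid for, plus edits to Section 4 and 8.1. The only downside is slightly more burden per survey.
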